1.1 Background

Motor vehicle collisions (MVCs) are one of the most common traumatic stress exposures in the US, and the most common for which individuals seek emergency department (ED) care. More than 1 million Black Americans (Blacks) come to the ED after MVC each year, and >90% of such ED MVC patients are discharged home with a diagnosis of acute musculoskeletal pain (MSP)/strain only. More than 80% of these individuals report acute moderate or severe (mod/sev) MSP in the ED, and >50% of those with acute mod/sev MSP transition to chronic MSP. MVCs, as well as pain after MVC, disproportionately affect Blacks vs. Whites. For example, in our previous cohort studies 67% of Blacks had mod/sev MSP six months after MVC, vs. only 40% of Whites. Interventions are urgently needed that prevent chronic MSP and reduce these MSP outcome disparities.

One safe, inexpensive, widely available, and well-tolerated intervention, with exciting potential to achieve these goals, is Vitamin D (Vitamin D). Vitamin D insufficiency is much more common in Blacks than Whites. In the investigators' previous observational study, 77% (103/133) of Black MVC survivors had Vitamin D insufficiency at the time of ED evaluation. Such low Vitamin D levels are associated with increased inflammation and worse pain outcomes. Vitamin D has anti-inflammatory, neuroprotective, and analgesic properties, and Vitamin D treatment improves pain outcomes in a range of conditions. Results of a recent Vitamin D intervention study in another trauma population (burn survivors) found that Vitamin D treatment after burn

injury disproportionately improved pain outcomes in Black vs. White burn survivors (67% vs. 33% pain improvement at 6 weeks). Results from a recent analysis suggest that Vitamin D administration in the ED after MVC could prevent at least 70,000 Blacks from developing chronic post-MVC MSP annually.

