3.2 Study Overview

Described the sequence of events in recruiting 90 patients in a multi-center randomized controlled trial. To assess a key primary outcome, we will enroll 50% white and 50% black MVC into the study. Each participant will be screened in based on a point of care Vitamin D test. This will be performed at the time of screening. Individuals with a Vitamin D level <100 ng/ml will be enrolled. Patients will be randomized 1:1 to receive a single dose of 300,000 IU of ergocalciferol versus placebo and followed for 3 months. At 3 months, patients will send a blood sample easily collected at home on a blood spot card to assess Vitamin D level 3 months following injury which is a key feasibility primary outcome.

Patients presenting to the ED within 24 hours of MVC (n=90, 45 non-Hispanic Black, and 45 non-Hispanic White) will receive a single dose of study drug prior to ED discharge (1:1 allocation 300,000 IU ergocalciferol or placebo). Prior to study drug administration, a baseline assessment will be performed (see below), and a fingerstick blood sample will be obtained to evaluate 25-hydroxyvitamin D level. Online survey follow-ups assessing primary and secondary outcomes and potential adverse events will be performed 3 weeks, 6 weeks, and 3 months after ED enrollment by study RAs using web-based REDCap™ software. Participants will also complete brief “flash-surveys” at the 2-week, 4-week, and 5-week timepoints using REDCap survey links. At 3 months, participants will also perform a fingerstick blood collection at home and mail the sample in a prepaid envelope to a lab to be processed to enable assessment of 3 month 25-hydroxyvitamin D concentration by treatment group.

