Analysis plan Overall efficacy (a) will be addressed by evaluating for evidence that Vitamin D administration per protocol vs. placebo decreases overall MSP scores across study timepoints. The effect of the intervention on overall pain over time will be assessed by evaluating the coefficient for treatment group (β_1) in the model: $P_{ij} = \beta_0 + \alpha_{0i} + \beta_1 \text{Treatment}_i + \beta_2 \text{Race}_i + \beta_3 (\text{Treatment} \times \text{Race}) + \varepsilon_{ij}$, where P_{ij} is the pain score for the i th individual at time point j , β 's denotes fixed effects, α_{0i} is the random intercept for the i th individual and ε corresponds to random errors. Narrowing of racial disparity will be addressed by evaluating the interaction between race and treatment (β_3 in model above). Specifically, as described above we will assess whether Vitamin D has greater effect on pain outcomes over time in Blacks than Whites. All analyses will be evaluated on the basis of intention to treat. Prior to

[figure not shown]

Figure 2. Plot demonstrating power to detect a main effect (β_1 , black lines) and interaction (β_3 , blue lines) across a range of sample sizes, at three effect sizes estimated using simulation data generated from previous studies. Vertical red line indicates sample size proposed here (n=90). This demonstrates the power to assess Aim 2a (black) and 2b (blue).

data un-blinding, the study statistician will perform a blind review of the data in which statistical models will be developed and tested using dummy (computer-generated) treatment assignments. This is to ensure important covariates are added to the model prior to un-blinding to eliminate any bias of model covariate selection on results. After un-blinding the data, we will use appropriately specified linear contrasts of model parameters to estimate mean differences between participants treated with Vitamin D and placebo and 95% confidence intervals.

Power Estimates of power were derived using a Monte Carlo simulation based on parameter estimates from our observational data of MVC survivors using R (v. 4.0.2⁴⁸); and the *simr* package (v. 1.0.5⁴⁹). The power across a range of effect sizes for the main effect (a) is shown in Figure 2. These data and analysis must be seen as general estimates given that we lack intervention data for this population/condition.

Secondary Analyses:

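### Overall efficacy is read from β1 in a model that also contains treatment × race, with no race coding stated; under 0/1 coding β1 is the effect in one race only

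*Combined protocol and SAP*

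**What the plan says.** Section 6.1 sets out a random-intercept model for the pain score with fixed effects for treatment (β1), race (β2) and treatment × race (β3). Aim (a) is an overall comparison of the arms: "Overall efficacy (a) will be addressed by evaluating for evidence that Vitamin D administration per protocol vs. placebo decreases overall MSP scores". The quantity named for it is β1: "The effect of the intervention on overall pain over time will be assessed by evaluating the coefficient for treatment group". Aim (b), narrowing of the racial disparity, is assessed by β3 in the same model: "we will assess whether Vitamin D has greater effect on pain outcomes over time in Blacks than Whites".

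The power text follows the same pairing: "The power across a range of effect sizes for the main effect (a) is shown in Figure 2". The Figure 2 caption labels β1 a main effect and adds: "This demonstrates the power to assess Aim 2a (black) and 2b (blue".

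For estimation after unblinding, section 6.1 says "we will use appropriately specified linear contrasts of model parameters to estimate mean differences between participants treated with Vitamin D and placebo". It gives no contrast weights. No section gives the coding or the reference level of race.

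The population for aim (a) is stated in two ways. The Study Summary (Objectives and Statistical Methodology rows) words it as the effect in Black Americans. Sections 2.1 and 6.1 carry no race restriction, and section 3.4 names both races.

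**The concern.** In a model with an interaction, the coefficient of treatment is the effect at the point where race equals zero. Whether that point is one of the two races or midway between them depends entirely on the coding. Two analysts could follow section 6.1 to the letter and report different quantities as overall efficacy: the effect in White participants, the effect in Black participants, or the average of the two.

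This matters more here than in most trials. The design is built around the possibility that β3 is not zero, which is the situation in which these three quantities differ. The Introduction and section 2.3 also say that the pilot's results, including its effect size, will be used to power a larger trial. That effect size is of limited use if its population is not fixed in advance.

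**Working it through.** **The plan's own figure.** The Figure 2 curves could not be read in the text available, and section 6.1 states no effect sizes, variances, alpha or power for the efficacy aims. Its power therefore cannot be reproduced. What follows is algebra on the stated model plus calculations under labelled assumptions.

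**Inputs from the documents.**
- The model in section 6.1.
- 90 participants: "45 non-Hispanic Black, and 45 non-Hispanic White" (section 3.2).
- 1:1 allocation (section 3.2).
- Four assessments: ED, 3 weeks, 6 weeks, 3 months (section 6.1).
- About 80% follow-up (section 6.1).

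**Assumed.** Two-sided alpha 0.05; arms balanced within race; intraclass correlation (ICC) 0.3, 0.5 or 0.7.

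**Step 1: what β1 is.** The treatment effect at race value r is β1 + β3·r.
- 0/1 coding: the effect is β1 in the race coded 0 and β1 + β3 in the race coded 1. The equal-weight average is β1 + ½β3, so β1 differs from it by ½β3.
- −½/+½ coding: the effects are β1 − ½β3 and β1 + ½β3, and their average is β1.

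**Step 2: precision.** Let σ² be the variance of a participant's mean score, with 90/4 = 22.5 participants per treatment-by-race cell.
- Effect in one race: σ²(1/22.5 + 1/22.5) = 0.0889σ².
- Average of two independent race-specific effects: ¼(0.0889 + 0.0889)σ² = 0.0444σ².
- Variance ratio 2; SE ratio √2 = 1.414.

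Exact generalised least squares for the random-intercept model, with 22 or 23 per cell and unit total SD, gives:

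| | ICC 0.3 | ICC 0.5 | ICC 0.7 |
|---|---|---|---|
| Complete data: SE of β1, 0/1 coding | 0.206 | 0.236 | 0.263 |
| Complete data: SE of β1 + ½β3 | 0.145 | 0.167 | 0.186 |
| 80% retained at 3 months: SE of β1, 0/1 coding | 0.211 | 0.240 | 0.265 |
| 80% retained at 3 months: SE of β1 + ½β3 | 0.149 | 0.170 | 0.187 |

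The ratio is 1.414 in every column. The 80% rows assume monotone loss spread evenly over the three follow-ups and equal in all four cells. The SE of β1 under −½/+½ coding equals that of β1 + ½β3 throughout.

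**Step 3: power with equal effects.** For 80% power the standardised effect is 1.960 + 0.842 = 2.802. Dividing by 1.414 gives 1.981, and Φ(1.981 − 1.960) = 50.8%. Starting from 90%, 70%, 60% or 50%, the same step gives 63%, 42%, 35% or 28%.

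**Step 4: unequal effects, illustration only.** The only Black/White response figures in the documents are the 67% and 33% improvement in burn survivors (section 1.1). Their average is (67 + 33)/2 = 50.
- White as reference: β1 would be 33/50 = 0.66 of the average. If the average had 80% power, β1 would have Φ(0.66 × 1.981 − 1.960), about 26%.
- Black as reference: β1 would be 67/50 = 1.34 of the average, with power Φ(1.34 × 1.981 − 1.960), about 76%.

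These figures come from a different population and are percentage improvements, not NRS differences from placebo.

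**Step 5: check by simulation.** One simulated data set, fitted as a mixed model under three codings that all comply with section 6.1:

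| Race coding | β1 | SE |
|---|---|---|
| White as reference | −0.840 | 0.451 |
| Black as reference | −0.684 | 0.451 |
| −½/+½ | −0.762 | 0.319 |

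β1 + ½β3 was −0.762 under either 0/1 coding.

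**The case against.** The strongest reply is that the defect is conditional. The plan never says 0/1. It calls β1 a main effect and uses it for overall efficacy, and centred coding is the coding that makes that language consistent. It also promises appropriately specified contrasts for estimation. Since reading off one coefficient needs no contrast, a combination such as β1 + ½β3 may be what was meant. Models are to be developed in a blind review, efficacy is preliminary, and the power figures are offered as general estimates.

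Part of this stands. What is shown is an undefined quantity, not a wrong analysis already carried out. If the Figure 2 simulation tested a 0/1-coded β1, its curves already include the larger SE. The burn-survivor ratio is not evidence about this trial. If the Study Summary's population governs, β1 with Black as the reference race is exactly the target. The race contrast also settles race weighting only: the model has no time term and includes the pre-dose ED score, and β1 + ½β3 leaves that as it is.

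It does not remove the point. Centred coding has to be inferred. The contrast sentence gives no weights and does not replace β1 as the quantity named for aim (a). The stated purpose of the blind review is covariate selection; it does not mention race coding or which effect is to be reported.

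**Conclusion.** The concern holds. As written, section 6.1 does not determine what overall efficacy means, and applying its β1 rule with 0/1 coding gives the effect in one race.

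Under that coding the SE is 1.414 times that of the average effect, given balanced cells and, with dropout, equal loss across cells. The fall from 80% to about 51% power also rests on an assumed starting power, an assumed alpha and equal effects in both races. If effects differ, β1 is off by ½β3, with the direction set by the reference race. Under −½/+½ coding there is no loss from this source. Nothing here shows that the Figure 2 power is wrong. This should be fixed before unblinding.

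**What to change.** 1. Reconcile the population for aim (a) between the Study Summary and sections 2.1, 3.4 and 6.1.
2. If it is overall, prespecify β1 + ½β3 under 0/1 coding as both test and estimate; equivalently, code race −½/+½ and use β1. Equal weights match the planned 45:45 enrolment. Keep β3 for aim (b), and report the effect in Black participants separately (β1 + β3 with Black coded 1 and White coded 0).
3. If it is Black Americans, name that contrast for aim (a) and report the average effect separately.
4. In either case, state the race coding and the contrast weights.
5. Confirm which parameter the Figure 2 main-effect curves powered, and restate them only if it was a different one.

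The cost is two or three sentences in section 6.1 and a check of the power code, with a re-run of the simulation only if step 5 calls for it. No new data are needed.

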Objectives	Assess the feasibility of administering a single dose of Vitamin D in the emergency department to Blacks and Whites presenting within 24 hours of MVC with moderate or severe musculoskeletal pain (MSP), along with the ability of this dose to achieve sustained increases in Vitamin D levels. Evaluate the potential efficacy of this intervention to improve MSP outcomes in Blacks and to reduce MSP disparities in Black vs. White MVC survivors.
Number of Subjects	90
Diagnosis and Main Inclusion Criteria	Presentation to emergency department (ED) within 24 hours of motor vehicle collision with an initial moderate/severe MSP severity (0-10 NRS of ≥ 4)
Study Product, Dose, Route, Regimen	Ergocalciferol (Vitamin D2), 300,000 IU (2-150,000 IU capsules) orally administered once as a single dose prior to discharge from emergency department
Duration of administration	One-time dose
Reference therapy	Matched placebo to Vitamin D preparation

Statistical Methodology	Assess the feasibility of the RCT protocol by (a) calculating recruitment rate and participant retention, and (b) measuring the ability of Vitamin D administration to generate sustained increases in whole-blood Vitamin D concentrations (assessed 3 months after MVC). Assess for preliminary efficacy that Vitamin D administration per protocol (a) decreases overall MSP severity in Black Americans during the 3 months following MVC, and (b) reduced MSP outcome disparities between Black vs. White Americans following MVC.
-------------------------	---

Introduction

This document is a protocol for a human research study. This study is to be conducted according to US and international standards of Good Clinical Practice (FDA Title 21 part 312 and International Conference on Harmonization guidelines), applicable government regulations and Institutional research policies and procedures.

The main objective of this study is to determine whether administration of a single dose of Vitamin D in the Emergency Department following a motor vehicle collision reduces racial disparities in chronic pain following a traumatic event. This phase II, multicenter, randomized controlled trial is a pilot study to determine feasibility and potential efficacy (effect size, sample variation, response to study drug, ability to reduce racial disparity in pain outcomes) that can be used to adequately power a larger randomized controlled trial to fully assess efficacy.

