1.4 Dose Rationale and Risk/Benefits

The dose of Ergocalciferol that we propose, 300,000 IU, has been shown to effectively raise Vitamin D concentration by ~9 ng/ml, and to raise serum 25 hydroxyvitamin D concentration above 30 ng/ml (Vitamin D sufficient levels) for over 3 months⁵. The ability of our single-dose protocol to raise Vitamin D will be a primary feasibility endpoint of this pilot study. Importantly, this dose is extremely well-tolerated: in previous trials, reports of side effects/adverse events is rare,⁶ many studies administering single, high-dose regimens report no side effects⁷⁻⁹, and the most common side effects have been mild GI complaints (e.g. nausea).⁶ Vitamin D administration has also been demonstrated to be safe, even among individuals who are already Vitamin D sufficient. ¹⁰⁻¹² Based on the Code of Federal Regulation (CFR), Ergocalciferol will be exempt from an investigational new drug (IND) application.^{5,13-16}

Chronic pain is associated with reduced mental and physical health and interferes with essential activities of daily life. Currently there are limited treatment options to address chronic pain once it has become established and the overarching aim of this clinical trial is to prevent chronic pain development, therefore there is a critical unmet need of safe, non-addictive, non-invasive preventative treatment options that can be administered to MVC survivors in the aftermath of an injury. This study has the potential to benefit participants and future MVC survivors and improve pain and general health outcomes. The risks of taking Vitamin D are small. Side effects from Vitamin D are rare, however, it is possible that over supplementation of Vitamin D may be associated with headache, loss of appetite, dry mouth, metallic taste, and nausea/vomiting.

The risks to the subjects in experiencing these side effects are balanced against the potential for a new, safe, non-opioid preventative treatment option for chronic pain following MVC.

Study Objectives

2.1 Primary Objective:

1. Assess the feasibility of the RCT protocol by (a) calculating recruitment rate and participant retention, and (b) measuring the ability of Vitamin D administration to generate sustained increases in whole-blood Vitamin D concentrations (assessed 3 months after MVC).

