2. To demonstrate the preliminary efficacy of Vitamin D administration per protocol on decreasing overall MSP severity during the 3 months following MVC, and reducing MSP outcome disparity between Blacks and Whites following MVC.

2.2 Secondary Objectives:

We will assess the effect of race and sex on treatment outcomes in secondary analyses. This will be accomplished using two analytic strategies. First, a sex X treatment interaction term (secondary analyses) will be entered into our statistical models to assess pain reduction in response to treatment. Second, a stratified analysis will be performed which will examine the influence of both sex and race on treatment effect on primary and secondary outcomes. Further, Secondary stratified analyses evaluate the influence of initial vitamin D level on treatment response. In addition, exploratory analyses on the relationship of vitamin D outcome and trajectory of pain as well as restricting analyses to participants with vitamin D deficiency at baseline will be performed. Secondary analyses will examine treatment effects adjusting for any baseline differences in psychosocial factors between treatment arms.

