6.1 Outcome definitions/Analysis plan/Power calculation

Assess the feasibility of the RCT protocol by (a) calculating recruitment rate and participant retention, and (b) measuring the ability of Vitamin D administration to generate sustained increases in whole-blood Vitamin D concentrations (assessed 3 months after MVC).

Outcome definitions for Feasibility will be determined by the ability of the study team to: recruit 90 patients into the trial over the 15-month recruitment period, retain >80% of participants through 3-month follow-up, and achieve Vitamin D levels >20 ng/ml in 90% of treatment group at 3-month follow-up. In addition, will determine whether Vitamin D

administration per protocol can raise Vitamin D concentration in treatment group > 10ng/ml above baseline.

Analyses: Feasibility analyses will be performed using descriptive statistics. To assess Vitamin D increase according to treatment group, paired t-test will be used.

Power: Based on our previous Vitamin D trial and other work,⁴⁰⁻⁴⁵ we estimate that observed follow-up will be ~80%. With n=90 sample, this will permit follow-up rates estimates at 3 months with 95% CI $\pm 8.3\%$. This will permit assessment of follow-up feasibility and necessary sample size for an R01 RCT, if pilot results warrant. In addition, based on our previous Vitamin D trial, assuming 80% retention and Vitamin D concentration standard deviation of 4ng/ml, we will have >99% power to detect a change of 10 ng/ml in Vitamin D level in the treatment group.

Assess **preliminary efficacy** of Vitamin D administration per protocol to (a) decrease overall MSP severity during the 3 months following MVC, and (b) reduce MSP outcome disparity between Blacks vs. Whites following MVC.

Outcome Definitions for Pain Reduction between treatment groups will be assessed using patient-reported overall MSP scores (0-10 NRS) obtained at the ED, 3-week, 6-week, and 3-month assessments. NRS scores are valid measures of pain assessment.^{46,47}

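### Chronic pain and its racial disparity are the stated question, but no planned analysis estimates a treatment effect on 3-month pain, the latest time measured

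*Combined protocol and SAP*

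**What the plan says.** The protocol describes its efficacy question in two ways.

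- **Chronic pain.** The title names racial disparity in chronic pain. The Introduction gives the main objective as whether a single ED dose "reduces racial disparities in chronic pain following a traumatic event". Section 1.4 says "the overarching aim of this clinical trial is to prevent chronic pain development". Section 2.3 plans a larger trial powered on chronic pain. The Background (1.1) sizes the disparity at a late time: "67% of Blacks had mod/sev MSP six months after MVC, vs. only 40% of Whites".
- **Pain over 3 months.** Objective 2 in section 2.1 concerns preliminary efficacy "on decreasing overall MSP severity during the 3 months following MVC", together with the Black-White disparity in pain outcome. The Study Summary and section 6.1 say much the same. Section 3.4 also names overall severity.

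The analysis follows the second description. The outcome in 6.1 is "patient-reported overall MSP scores (0-10 NRS) obtained at the ED, 3-week, 6-week, and 3-month assessments". The model contains treatment, race, treatment x race and a random intercept per person. Efficacy is read from the treatment coefficient (β1): "The effect of the intervention on overall pain over time will be assessed by evaluating the coefficient for treatment group". Narrowing of disparity is read from the treatment x race coefficient (β3). Linear contrasts of the model parameters are planned after unblinding. The secondary analyses fit models of similar form to the Brief Pain Inventory and SF-12 and add a sex interaction. Section 2.2 adds stratified analyses and an exploratory look at vitamin D outcome and pain trajectory.

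**The concern.** The model has no visit term and no treatment-by-visit term, so none of its parameters belongs to a particular time. The planned linear contrasts can combine only those parameters and cannot isolate 3 months. No section defines chronic pain as an outcome, and none specifies a treatment contrast on pain at the last visit.

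This affects what the trial can conclude. A single dose might ease pain for some weeks, or it might reduce the pain that persists. Only the second bears on the question in the title and Introduction. A pooled coefficient cannot tell a reader which occurred, either overall or for the racial gap. The Introduction also says the pilot is meant to supply effect size and variation for a larger trial, and 2.3 describes that trial in terms of chronic pain. The plan prespecifies no estimate of that kind.

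**Working it through.** **The plan's own figure.** Section 6.1 gives a 95% CI of ±8.3% for follow-up at 80% with n = 90. Check: 1.96 × √(0.8 × 0.2 / 90) = 0.0826, so it reproduces. It implies 0.8 × 90 = 72 retained: 36 per arm at 1:1 allocation, and 18 per race-by-arm cell with equal numbers by race. Power for pain appears only in Figure 2, which is not in the text available. No stated number is disputed here.

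**What the pooled coefficient measures.** With complete data and a random intercept, a treatment coefficient that is constant over time equals the simple mean of the visit-specific effects. There are four scores. The ED score is taken before dosing (3.2), so its expected treatment effect is 0.

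| True effect (ED, 3 wk, 6 wk, 3 mo) | Coefficient as written | ED score removed |
|---|---|---|
| 0, 1, 1, 1 | 3/4 = 0.75 | 3/3 = 1 |
| 0, 0, 0, 1 (late only) | 1/4 = 0.25 | 1/3 |
| 0, 1, 1, 0 (early only) | 2/4 = 0.50 | 2/3 |

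The treatment with no benefit at 3 months gives twice the coefficient of the one acting only at 3 months. Removing the ED score does not change that ratio. The same weights apply to β3. They also apply to β1 whether race is coded so that β1 is an average or the effect in one race group; the coding is not stated.

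**With 80% having the 3-month score.** Assume the other 20% have the first three scores, and let ρ be the within-person correlation (assumed). A person with k scores contributes the sum of their effects divided by 1 + (k − 1)ρ. At ρ = 0.5:

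- Denominator: 0.8 × 4/2.5 + 0.2 × 3/2 = 1.58
- Late only: (0.8 × 1/2.5) / 1.58 = 0.20
- Early only: (0.8 × 2/2.5 + 0.2 × 2/2) / 1.58 = 0.53

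Values of ρ from 0.3 to 0.7 give the same results to two decimals.

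**Precision of a 3-month contrast.** The text gives no pain SD, so an NRS SD of 2 to 3 is assumed, with no gain from baseline adjustment.

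| 95% CI half-width | SD 2 | SD 2.5 | SD 3 |
|---|---|---|---|
| Treatment: 1.96 × SD × √(2/36) | 0.92 | 1.15 | 1.39 |
| Treatment x race: 1.96 × SD × √(4/18) | 1.85 | 2.31 | 2.77 |

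For the proportion with NRS ≥4 at 3 months, assuming 50%:

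- Treatment: 1.96 × √(2 × 0.25/36) = 0.231, about ±23 points
- Treatment x race: 1.96 × √(4 × 0.25/18) = 0.462, about ±46 points

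The second is wider than the gap cited in the Background, 67 − 40 = 27 points, which was itself measured at 6 months.

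**The case against.** The strongest reply is that the formal objective is already served. Section 2.1 asks about overall severity during the 3 months, and a time average roughly matches that. This stands: the model does not miss its formal objective. The mismatch is with the title, Introduction, 1.4 and 2.3, and rewording the Introduction and 1.4 is a legitimate remedy. The absent time term and the pooled pre-dose score are separate modelling questions.

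A reader might infer that a single coefficient is the only efficacy result. The documents do not support that: β3 is specified for disparity, and secondary, stratified and exploratory analyses follow. None of these is specified as a randomized comparison of pain at 3 months.

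A reader might also infer that an early and a late effect always give the same coefficient. They do so only in special cases, such as equal effects each confined to one post-dose visit with complete data. In general the coefficient simply does not reveal timing.

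Nor will the larger trial necessarily lack an effect size. The 3-month NRS is collected, and 2.3 says the collected data will be used for design. What is missing is a prespecified estimate.

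The blinded model review in 6.1 might add terms, but it is described as selecting covariates, and no time-specific estimate is named. Finally, this is a small pilot whose efficacy aim is called preliminary. That limits what a late contrast can show and argues for reporting it as an estimate with its CI, without a test-based claim.

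**Conclusion.** The concern holds as a gap between the stated question and the planned estimates. Both efficacy coefficients pool ED, 3-week, 6-week and 3-month pain, and no planned analysis estimates a treatment effect on 3-month pain or on the racial gap in it. As written, a 1-point late-only effect appears as 0.25 and a 1-point early-only effect as 0.50; at 80% retention these are about 0.20 and 0.53. The complete-data figures need only the random-intercept form and balanced visits. The retention figures also assume the dropout pattern and correlations stated above.

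It would be tempting to conclude that the pilot can say nothing about late pain. That goes too far: the data will exist, and an estimate can be planned now at little cost. Even so, the disparity estimate at 3 months would be descriptive only, and nothing in this trial reaches the 6-month horizon of the cited gap.

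**What to change.** In sections 3.4 and 6.1:

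1. Keep the time-averaged effect as the estimate for objective 2.1, written as an explicit contrast.
2. Add visit and its interactions with treatment and race to the mixed model.
3. Prespecify the 3-month treatment contrast and the 3-month treatment x race contrast, each with a 95% CI. State that any conclusion about chronic pain rests on these and extends only to 3 months.
4. Optionally, add a descriptive table by race and arm of the share with NRS ≥4 at 3 months, with CIs. The protocol uses this cutoff for moderate or severe pain at entry but does not define it as chronic pain, so the table should be labelled accordingly.

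If the contrasts are not added, restate the Introduction and 1.4 so that the objective is pain severity over 3 months.

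The cost is analysis wording, extra model terms and, if used, one table. No visit, participant or procedure changes. The price is lower precision than the time average and a narrower claim about chronic pain.
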